3.3 WITHDRAWAL OF SUBJECTS

Each subject may voluntarily withdraw his/her participation from the study at any time without jeopardy or prejudice. If a subject prematurely terminates from the study, the reason for study termination will be recorded and the results will be tabulated by number and percent for each category. If termination is a result of an adverse event or death, an Adverse Event Form will also be completed. Subjects who withdraw consent after treatment will have their data evaluated until the time of their withdrawal.

The Investigator should follow all unresolved serious adverse events until the events are resolved, the subject is lost to follow-up, the subject has withdrawn consent, the subject completes the study, or the adverse event is otherwise explained.

All reasonable efforts will be made to obtain complete data for all subjects; however, missing observations will occur due to loss to follow-up, withdrawal, or non-adherence with required assessments. Three attempts shall be made to contact subjects who do not return for study follow-up visits. The final attempt shall include a certified letter to the subject regarding study participation. If these subjects cannot be located at the final scheduled visit, they will be considered lost to follow-up. If they are contacted but refuse to return for visits, they will be considered withdrawals. Subjects shall be encouraged to complete a final study exit visit at the time of withdrawal to assess for safety. Data collected up to the time of loss to follow-up or withdrawal will be maintained in the study database and used for analysis purposes, as appropriate. These subjects will not be replaced.

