4.8 ENROLLMENT

According to ISO 14155:2011, enrollment in the study occurs at the time of informed consent; however, for the purposes of this study, only subjects who are consented and meet all the study inclusion criteria and none of the study exclusion criteria, venous and arterial access has been achieved and study device advanced beyond the sheath will be considered enrolled into the study. Therefore, the enrollment date (Day 0) will be the date of the study index procedure; the enrollment date will not be the date of informed consent for this study. Subjects in whom the PQ Bypass System is inserted into the vascular and/or the procedure was aborted without treatment with the device shall be followed through discharge for safety only and allowed to exit the study.

Investigators will access the target artery and the corresponding ipsilateral vein using standard percutaneous techniques and devices. Patient eligibility will be confirmed prior to insertion of the study device, based on procedural angiogram and sheath placement.

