7.1.1. Primary Effectiveness

The primary effectiveness endpoint is defined as primary patency at 12 months as evidenced by a peak systolic velocity ratio (PSVR) ≤ 2.5 from DUS and no clinically-driven re-intervention within the stented segment.

The primary effectiveness endpoint hypotheses are:

- H0: 12-month success rate of the PQ Bypass System $\leq 60.4\%$
- HA: 12-month success rate of the PQ Bypass System $> 60.4\%$

Based on a PG of 60.4%, a sample size of 202 with 181 subjects having evaluable data at 12 months would provide 91% power to test the primary effective hypothesis at the one-sided alpha level of 0.025, if the “true” PQ Bypass Stent Graft success rate is at least 72%. The Exact Test Method and commercial software PASS14 was used to determine the sample size.

In order to ensure sufficient subjects are available at 12 months for assessment of the primary effectiveness endpoint (i.e., to account for missing data), an additional 21 subjects (approximately 10% estimated attrition rate) may be enrolled, making the total study sample size equal to 202 TASC II D and complex TASC C subjects.

To meet the primary effectiveness endpoint of the IDE Study with a sample size of 202 enrolled and 181 evaluable subjects with 12 month primary patency data, at least 124 subjects ($\geq 68.1\%$) must experience 12-month primary patency (calculated using the exact confidence interval).

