7.3.1. Missing Data

Subjects free from clinically-driven target lesion revascularization within the stented segment but do not have sufficient follow-up to assess the primary effectiveness endpoint will be treated as having missing data for the primary effectiveness endpoint. To further evaluate the impact of missing data on the primary

effectiveness endpoint, Kaplan-Meier methods, will also be used to estimate the 12-month primary patency rate.

For the primary safety endpoint analysis, the denominator for each parameter in the safety measures will be the number of subjects who had sufficient follow up (at least 23 days for 30-day visit) plus any subjects who had an event prior to the milestone visit.

All subjects will be accounted for in the study report, including the reasons for any subjects exiting the study early.

Every effort will be made to collect all data points contributing to the primary effectiveness endpoint in the study. The sponsor attempts to minimize the amount of missing data by appropriate management of the prospective clinical trial, proper screening of study subjects, and training of participating investigators, monitors and study coordinators. In order to further assess the potential impact of missing data on the primary effectiveness endpoint analyses, the following sensitivity analyses will be performed:

- Worst-Case Scenario: Each missing value for the primary effectiveness endpoint will be treated as a failure. If this still results in rejection of the null hypothesis then no further missing data imputation analyses will be performed for the endpoint.
- If the conclusion is not upheld with the worst-case scenario approach, then the multiple imputation method will be used. A logistic regression model will be used and fifteen imputed datasets will be generated.
- Additionally a tipping point analysis will be performed. The proportion of missing values assigned the status of 'failure' will be sequentially increased to identify the point at which the study conclusions change (i.e., the null hypothesis is no longer rejected).

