7.4 EFFICACY ANALYSES

7.4.1. Primary Effectiveness Analysis

The MITT cohort will be used to evaluate the primary effectiveness endpoint. All subjects in the MITT population that have a clinically-driven re-intervention within the stented segment that occurs within 360 days of the index procedure will be considered a failure for the primary effectiveness endpoint. All subjects free from clinically-driven re-intervention within the

stented segment who meet the definition of stent graft patency with at least 11 months (330 days) of follow-up will be considered successful with respect to the primary effectiveness endpoint. Subjects free from clinically-driven re-intervention within the stented segment but do not have sufficient follow-up to assess the primary effectiveness endpoint will be treated as missing data.

The primary effectiveness hypothesis will be tested by calculating the one-sided 97.5% confidence limit, using the Exact method. If the lower limit exceeds the performance goal of 60.4% the primary effectiveness hypothesis will be met.

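### The 91% power in sections 5.1 and 7.1.1 takes the 21 planned losses as neutral, but under 7.4.1 an early leaver can be a failure or missing, never a success; if 72% is the true rate in all implanted subjects, power at full attrition is about 82-87%

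*Combined protocol and SAP*

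**What the plan says.** Section 7.4.1 sorts implanted (MITT) subjects into three groups.

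- Failure: clinically-driven repeat treatment of the stented segment. A subject in whom this "occurs within 360 days of the index procedure will be considered a failure for the primary effectiveness endpoint". No minimum follow-up applies.
- Success: subjects free of re-intervention "who meet the definition of stent graft patency with at least 11 months (330 days) of follow-up will be considered successful".
- Missing: subjects free of re-intervention who "do not have sufficient follow-up to assess the primary effectiveness endpoint will be treated as missing data".

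The primary test compares the exact lower one-sided 97.5% limit of this proportion with the performance goal of 60.4%.

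Section 7.1.1 says that 202 subjects with 181 evaluable "would provide 91% power to test the primary effective hypothesis at the one-sided alpha level of 0.025" if the success rate, which it describes as the true one, is at least 72%. To cover missing data, "an additional 21 subjects (approximately 10% estimated attrition rate) may be enrolled". Section 5.1 gives the same power without the word true.

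Section 7.3.1 adds that "Kaplan-Meier methods, will also be used to estimate the 12-month primary patency rate", together with worst-case, multiple-imputation and tipping-point analyses. The primary test is unchanged by these, and no section adjusts the power for the counting rule.

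**The concern.** The failure and success rules ask for different amounts of follow-up. Suppose two subjects both withdraw at day 200. If one was re-intervened at day 150, that subject stays in the denominator as a failure. If the other has a patent graft, that subject drops out. Early exits can thus add failures to the primary proportion but cannot add successes.

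The power calculation has no such feature. It removes 21 subjects and leaves the rate among the remaining 181 at 72%. That is right if no leaver had been re-intervened before exit, or if 72% was meant from the start as the rate among subjects evaluable under 7.4.1. It is not right if 72% is the true 12-month patency in everyone implanted, which is how 7.1.1 reads most naturally.

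At stake is the sponsor's own risk of missing the goal with a device that performs as planned, and the reading of a narrow miss, part of which could then come from the counting rule.

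**Working it through.** **Inputs from the documents.** Goal 60.4%, rate 72%, 181 evaluable, 21 losses, one-sided alpha 0.025, exact test (7.1.1); classification rules and exact limit (7.4.1).

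**Assumptions, because the documents give no figures.** Exits are unrelated to outcome and uniform over days 0-330. The share *s* of patency failures that are re-interventions runs from 50% to 100%. Re-interventions are either uniform over days 0-360, or 25% fall by day 30 with the rest uniform after that. As a rough guide, DETOUR I (section 1.5) had 5 of 19 target vessel revascularizations by day 30 (26%), and 19 revascularizations against 21 of 80 limbs not patent (90%). Target vessel revascularization is not the same as clinically-driven target lesion revascularization, so these figures are only indicative.

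**Step 1, the plan's own figure.** The smallest count out of 181 with exact tail probability at 60.4% no greater than 0.025 is 123 (tail 0.0216, lower limit 60.6%). P(X ≥ 123) for X ~ Binomial(181, 0.72) is 0.901, close to the stated 91%.

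**Step 2, chance that a leaver enters as a failure.** q = 0.28 × s × P, where P is the chance that a re-intervention precedes the exit.

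- Uniform re-interventions: P = mean exit day / 360 = 165/360 = 0.458.
- 25% by day 30: P = [30 × 0.125 + 300 × (0.25 + 0.75 × 150/330)] / 330 = 0.549.

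**Step 3, power.** There are 181 stayers with Binomial(181, 0.72) successes. The number *k* of leavers counted as failures is Binomial(21, q). The exact critical value is recomputed for each denominator 181 + k (for example 123/181, 124/182, 125/184, 126/186), and power is summed over k. The expected evaluable rate is approximately 181 × 0.72 / (181 + 21q).

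| Timing | s | 21q | Evaluable rate | Power |
|---|---|---|---|---|
| No leaver re-intervened | – | 0 | 72.0% | 90.1% |
| Uniform | 100% | 2.7 | 70.9% | 83.7% |
| Uniform | 50% | 1.3 | 71.5% | 87.0% |
| 25% by day 30 | 100% | 3.2 | 70.7% | 82.2% |
| 25% by day 30 | 90% | 2.9 | 70.9% | 83.2% |
| 25% by day 30 | 50% | 1.6 | 71.4% | 86.4% |

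**Step 4, dependence on the number of losses and the true rate.**

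- 10 losses of 202: 89-90%.
- 2 or 3 losses: 91-93%. DETOUR I assessed one-year patency in 80 of 81 limbs; 202 × 1/81 ≈ 2.5 losses.
- True rate 73.8% (the DETOUR I rate), 21 spread losses: 93-95%.
- True rate that restores 90.1% with 21 spread losses: 72.5-73.2%.
- Type I error at 60.4% with 21 spread losses: 0.7-1.4%.

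**Step 5, the stated threshold.** Both sections ask for at least 124 successes and give 68.1%. But 124/181 = 68.5%; 68.1% is 124/182. A rule of 124 out of 181 has power P(X ≥ 124) = 87.0%, not 90% or 91%. Section 5.1 also names 191 evaluable subjects in this sentence where 7.1.1 has 181.

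**The case against.** The strongest reply is that the stated power is conditional and its condition is met. Section 7.1.1 gives power for 181 evaluable subjects, success is defined operationally only in 7.4.1, and a leaver already re-intervened is evaluable there. If 72% is the rate in that group, 90% is correct and nothing is misstated. This stands as a possible reading. The text does not say it is the intended one, and the word true in 7.1.1 points the other way.

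The 82-87% band also needs the whole allowance of 21 to be used and rests on exit timing and a re-intervention share that the documents do not give. DETOUR I had about 1% missing, where the effect vanishes, and at its 73.8% patency the power exceeds 91% even with 21 losses. Some losses are neutral or recoverable. Cases where the "procedure was aborted without treatment with the device shall be followed through discharge for safety only and allowed to exit the study" fall outside MITT: if 3 of the 21 are of this kind, power is 84-87%. Section 3.3 declares loss late ("If these subjects cannot be located at the final scheduled visit, they will be considered lost to follow-up"), and 7.4.1 sets no upper limit on follow-up, so a missed 12-month visit may be resolved by later imaging. All of this stands and limits the point.

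The analyses in 7.3.1 address missing data, but none of them changes the primary test or the stated power.

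Two stronger readings do not hold. A reader might infer that every early leaver is counted as a failure. Section 7.4.1 makes most of them missing; only about 1.3 to 3.2 of the 21 are expected to enter as failures. A reader might also infer that the rule flatters the device or makes a positive result unsafe. The bias runs against the device, and type I error falls below the nominal 2.5%.

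**Conclusion.** The asymmetry in 7.4.1 is real, and the power statement does not account for it. The 91% is reproduced, to within about a point, when 72% is the success rate among subjects evaluable under 7.4.1. If 72% is instead the true rate in all implanted subjects, and all 21 losses occur before day 330, evenly spread and unrelated to outcome, exact power is about 82-87% with 50-100% of failures being re-interventions. The chance of missing the goal is then about 13-18%, against the planned 9%. The effect is small at 10 losses and absent at 2 or 3.

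This is a minor point: a restatement of the power figure. It does not show that the sample size is inadequate, and it does not weaken a positive result. The separate mismatch in the 124-subject threshold needs none of these assumptions and should be corrected at the same time.

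**What to change.** In sections 5.1 and 7.1.1:

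1. State that the power figure is conditional on a 72% success rate among subjects evaluable under 7.4.1, where exact power is 90% with a critical value of 123 out of 181.
2. Reconcile this with the threshold of 124 subjects and 68.1%, since 124/181 is 68.5% and a 124 rule gives 87% power. Align the 191 in 5.1 with the 181 in 7.1.1.
3. Add that if 72% is the true rate in all implanted subjects, power at the full 10% attrition is about 82-87%, and state the assumptions on exit timing and re-intervention share.

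Keep the exact proportion as the primary test. Report the Kaplan-Meier estimate already planned in 7.3.1 beside it, read at day 360, with subjects patent at the 12-month scan carried to day 360. In a simulation of 4,000 trials with 21 spread exits, scans uniform over days 330-390 and a log-log limit, carrying patent subjects forward gave a mean estimate of 71.9-72.1% and power of 90-91%. Censoring them at the scan date gave means from 71.1% to 76.5%, depending on the re-intervention share, so the handling should be stated.

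The cost is wording in 5.1, 7.1.1 and 7.3.1. No new data, added enrolment or change of primary test is needed. The downside is a less favourable stated power.

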4.2 TRIAL ENDPOINTS

4.2.1 Primary Effectiveness Endpoint

The absence of clinically-driven target lesion revascularization and absence of recurrent target lesion diameter stenosis >50% by imaging (e.g., duplex ultrasound (peak systolic velocity ratio of

>2.5) or invasive angiography) with the stent or immediately 1 cm above or below the treated segment. When both modalities are available, angiography takes precedence..

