Major Adverse Event (MAE): An MAE comprises the following: Death, Clinically-Driven Target Lesion Revascularization (CD-TLR), Amputation of the Treated Limb, Symptomatic Deep Vein Thrombosis (DVT), Pulmonary Embolism, or procedure-related bleeding requiring any transfusion of packed red blood cells or surgery.

Major Adverse Limb Events (MALE): A Major Adverse Limb Event (MALE) defined as above-ankle amputation or major reintervention including placement of a new bypass graft, interposition graft, thrombectomy, or thrombolysis.

Myocardial Infarction (MI): Evidence of myocardial necrosis in a clinical setting consistent with myocardial ischemia, requiring a combination of evidence of myocardial necrosis [either changes in cardiac biomarkers (e.g., troponins or CK-MB) or post-mortem pathological findings] and supporting information derived from the clinical presentation, electrocardiographic changes, or the results of myocardial or coronary artery imaging.

Patency, Primary Vessel: Vessel patency at a given time point will be determined by the absence of clinically-driven target lesion revascularization and absence of recurrent target lesion diameter stenosis > 50% by imaging (e.g., invasive angiography or most commonly, duplex ultrasonography). Luminal diameter is assessed by core lab using angiography or duplex ultrasound imaging. Loss of primary stent patency is deemed when peak systolic velocity ratio (PSVR) is >2.5, or where angiography reveals >50% diameter stenosis, or where the subject undergoes clinically-driven TLR. When both imaging modalities are available, angiography takes precedence.

Patency, Tibioperoneal Run-Off: Subject has at least one patent tibioperoneal run-off vessel with <50% stenosis confirmed by angiography at time of enrollment.

Perforation: Puncture of an arterial wall.

Pseudoaneurysm: Disruption of the arterial wall characterized by an out-pouching or pocket with swirling, flowing blood outside of the confines of the arterial lumen.

Recurrent Occlusion: Occlusion (i.e., total obstruction of vessel lumen) after a successful canalization.

Recurrent Thrombosis: Thrombosis (i.e. sub-total obstruction of vessel lumen) following successful treatment.

Reference Vessel Diameter, Proximal (RVD_{prox}): Diameter of normal vessel immediately proximal to the treated segment.

Reference Vessel Diameter, Distal (RVD_{dist}): Diameter of normal vessel immediately distal to the treated segment.

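### Section 7.4.1 has no failure branch for loss of patency on imaging, so read literally an early core-lab loss followed by exit before day 330 drops out of the primary denominator

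*Combined protocol and SAP*

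**What the plan says.** Section 7.4.1 sorts the MITT subjects into three groups.

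- Failure: subjects "that have a clinically-driven re-intervention within the stented segment that occurs within 360 days of the index procedure will be considered a failure".
- Success: subjects free of such a re-intervention in the "stented segment who meet the definition of stent graft patency with at least 11 months (330 days) of follow-up will be considered successful".
- Missing: subjects free of such a re-intervention "within the stented segment but do not have sufficient follow-up to assess the primary effectiveness endpoint will be treated as missing data".

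Section 7.3.1 repeats the third rule in nearly the same words, saying target lesion revascularization instead of re-intervention. These subjects "will be treated as having missing data for the primary effectiveness endpoint".

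The endpoint itself is wider than re-intervention. Section 4.2.1 also requires "absence of recurrent target lesion diameter stenosis >50% by imaging", and Section 15 (Patency, Primary Vessel) adds: "Loss of primary stent patency is deemed when peak systolic velocity ratio (PSVR) is >2.5", or when angiography shows more than 50% stenosis.

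For the 30-day safety endpoint, Section 7.3.1 defines the denominator as subjects with enough follow-up "plus any subjects who had an event prior to the milestone visit". The effectiveness rule has no matching clause.

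**The concern.** Duplex ultrasound is scheduled at every follow-up visit (Table 1, footnote 4), so losses of patency will be recorded at 1 and 6 months. Take a subject with such a loss, no clinically-driven re-intervention, and exit before day 330. The failure branch does not apply, because there was no re-intervention. The success branch does not apply, because the graft is not patent and follow-up is too short. Only the missing branch is left, and it removes from the denominator a subject who has met the plan's own definition of lost patency.

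The primary test is a single exact limit against a fixed goal, in a single-arm study without a masked comparator. If the wording permits two classifications, the choice could be made after the outcomes are known.

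**Working it through.** **Inputs.** Goal 60.4%, assumed true rate 72%, one-sided alpha 0.025, 181 evaluable of 202 enrolled, 21 lost (Section 7.1.1). Decision rule: the exact lower one-sided 97.5% limit must exceed 60.4% (Section 7.4.1).

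**Reproducing the plan.** The exact lower limit for x successes in n is the 0.025 quantile of Beta(x, n − x + 1). At n = 181 the smallest passing count is 123 (limit 60.63%; 122 gives 60.05%). Section 7.1.1 prints 124. With cut-off 123, P(X ≥ 123) is 2.2% at a true 60.4% and 90.1% at 72%. The one-sample z formula with the null variance gives 91.0% power, so the stated 91% is reproduced.

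**Effect of one subject.** Suppose 122 successes and 59 failures, one of the failures being an early imaging loss that exits before day 330.

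- Counted as a failure: 122/181, limit 60.05%, fails.
- Classed as missing: 122/180, limit 60.42%, passes.

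**Further from the boundary.** Start from the literal-rule result and add k such subjects back as failures.

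| Literal-rule result | Largest k that still passes | First k that fails |
|---|---|---|
| 123/181 (60.63%) | 0 | 1: 123/182 (60.26%) |
| 124/181 (61.20%) | 2: 124/183 (60.47%) | 3: 124/184 (60.11%) |
| 130/181 (64.67%) | 11: 130/192 (60.60%) | 12: 130/193 (60.25%) |

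Near the expected result (130/181 = 71.8%) it would take 12 such subjects to reverse the conclusion.

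**How many to expect.** The documents give no count. One illustrative figure uses the earlier study (Section 1.5): 80 − 59 = 21 limbs not patent at one year, of which at most 19 had target vessel revascularization, leaving at least 2 of 80 (2.5%) with loss and no such repair. If these exit at the planned rate, 21/202 = 10.4%, then 202 × 0.025 × 0.104 ≈ 0.5 subject. Those limbs were in the one-year denominator, so they show that such losses occur, not that they exit early.

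**Direction against the truth.** Assume a true rate of 72%, random exit of 10.4%, 2.5% imaging-only loss, and every re-intervention failure kept (a bounding assumption). Observed successes are 0.72 × 0.896 = 0.645 of those enrolled.

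- As written: missing 0.104 × (0.72 + 0.025) = 0.077, evaluable 0.923, expected observed rate 69.9%.
- With early imaging losses counted: missing 0.104 × 0.72 = 0.075, evaluable 0.925, expected observed rate 69.7%.

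With the cut-off re-derived for each n, power is about 76% as written and about 74% with the losses counted. Both observed rates lie below the true 72%, because patent early exits are dropped while early re-intervention failures are kept.

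**The case against.** **An observed loss may already be an assessment.** The missing rule applies only where follow-up is too short to assess the endpoint, the 330 days qualify only the success sentence, and Section 15 deems patency lost once the PSVR threshold is crossed. This reading is tenable, and on it nothing is lost. But it is not written. The only follow-up length given for this endpoint is 330 days, Section 7.1.1 defines the endpoint at 12 months, and the clause that keeps early events appears for safety alone.

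**An early raised PSVR may not persist.** If a reading can revert, status at 12 months is unknown after early exit, and missing is defensible. This stands as a caution. It is a reason not to fail an unrepaired subject who is patent at the 12-month assessment. It does not justify leaving the classification of early exits open.

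**The sensitivity analyses cover it.** In the worst case, "Each missing value for the primary effectiveness endpoint will be treated as a failure", and tipping-point, imputation and Kaplan-Meier analyses are also planned. They would expose a fragile result, but they do not decide the primary test.

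**A reader might infer inflated type I error, or a rule that always flatters the device.** The documents support neither. A calculation that removes only failures ignores that patent early exits also become missing. If all subjects leave at the same rate whatever their status, the evaluable rate stays at the true rate and the false-pass probability stays near its nominal level. Under the illustrative assumptions above, with the true rate set to 60.4%, it is about 0.3% as written. An excess would need subjects with imaging loss to exit more often than patent subjects, and nothing in the documents shows that.

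**Conclusion.** The gap is real. No branch of 7.4.1 or 7.3.1 makes imaging loss a failure, and the literal missing rule conflicts with the endpoint in Sections 4.2.1 and 15. Relative to counting these subjects as failures, it can only raise the observed rate. Relative to the true rate, its direction depends on exit patterns that the documents do not give, and no type I error figure is claimed. The number affected is unknown and probably small: about half a subject under the illustrative shares, which are assumptions. The point matters because one subject can decide a boundary result and the classification can be settled in advance by wording.

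A reader might also infer that subjects with imaging loss who are followed past day 330 are dropped. The text does not support that: they fit neither the success nor the missing branch and are presumably failures, although this too is unwritten.

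**What to change.** In Sections 7.4.1 and 7.3.1, state that a subject who exits before the 12-month assessment, and whose last evaluable core-lab imaging shows loss of primary patency as defined in Section 15 (angiography taking precedence), is a failure and stays in the denominator. Define the denominator as subjects with sufficient follow-up plus those with an earlier failure, parallel to the safety rule. Do not extend this to an unrepaired subject with an early raised PSVR who is patent at the 12-month assessment.

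The change is wording only and needs no new visits or imaging. Its downside should be disclosed: early exits whose last imaging shows loss are counted while patent early exits stay missing, so the observed rate and power fall slightly even when exit is random (about 74% against 76% in the illustration above). Most of the distance from the 90.1% design power in that illustration comes from the existing treatment of early re-interventions, not from this change. The asymmetry matches how the plan already handles early re-interventions and early safety events.
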